Conducting a beta test to confirm the protocol, including the software functionality and surveys. Before rolling out the RCT, we may conduct a beta test to pilot the recruitment, enrollment, data collection, and randomization procedures, as well as to identify final opportunities to improve the content. In most cases, five is a sufficient number of testers to identify any issues. Here, we propose 15-20 youth so that ~10 youth will test the functionality of the intervention program and ~5 the functionality of the control program. Usability data will be collected weekly via text messaging from participants. We may send questions weekly via text messaging, or by phone for non-responders, about the program experience. At the end of the beta test, we may conduct one-on-one interviews to identify any additional experiential issues that need to be addressed before the RCT is launched.

Pilot RCT of BullyDown (n = 150)

Randomization and group assignment. Once youth complete the baseline survey, they will be randomly assigned to either the intervention (n = 76) or the control (n = 74) group. We will use a computerized minimization technique, as originally described by Taves⁵⁹ and more recently reviewed by others,⁶⁰⁻⁶² to balance the sample on youth key indicators. These may include sex, school or Club, and bullying perpetration history. Treatment assignment will be generated and maintained at a password-protected Internet website monitored by [name].

Contamination. Studies across participant populations and behavioral targets report that contamination is uncommon and does not affect study outcomes.^{63,64,65,66} Give this, and to be efficient with R21 resources, students will be randomized at the individual rather than school or Club level. As we have done previously,^{63,64} we will ask questions at intervention end that are specific to the BullyDown content. If indicated, we will include the number of correct exposure

questions as a proxy for contamination in multivariate models.

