Preliminary behavioral outcome measures (Intervention end and 3-month follow-up)	Bullying perpetration	Bullying will be queried by type (e.g., relational, physical), mode (e.g., online, in-person), and place (e.g., at home, at school). ⁶⁸ Youth who endorse any question at a frequency of 3 times or more in the past 30 days (to reflect repetitive behavior) will be coded as engaging in bullying.
	Other aggression	Youth who report engaging in the above bullying perpetration items, but less frequently so, will be coded as engaging in aggressive acts. ⁶⁸
	Bystander behavior	Youth will be asked if, in the past 30 days, they have seen or heard about (e.g., as a rumor) someone being bullied. Those who say yes will be asked what they did in response. Options will include: nothing, telling an adult, talking to the victim, and standing up to the bully.

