Transcripts of the FGs will be entered into Dedoose (formerly EthnoNotes),⁸⁵ a mixed methods analysis program. Codes will be generated based on the first FG, reexamined, and refined through constant comparison with the second FG.⁸⁶ A codebook will be created with codes, brief descriptions, and illustrative quotations.⁸⁷ Codes will be both generated inductively and derived from our initial research questions (e.g., how youth interact with their peers and their teacher online). [name] project coordinator and [name] graduate research assistant will code both FGs. To assure inter-coder reliability, we will calculate a kappa value and accept a minimum of 0.75 as the criterion for adequate agreement between coders.⁸⁸ After coding is complete, we will extract themes using an iterative process to highlight evidence contradictory to our conclusions as well as the modal response.⁸⁹ The analysis will result in a report that describes the findings and advises how to integrate them into program content.

Specific Aim 2: Pilot test the 7-week BullyDown intervention for feasibility and acceptability in an RCT of 150 adolescents either in middle school and/or 12-14 years of age.

The **feasibility** of the BullyDown intervention will be determined by our recruitment and retention rates. If at least 75% of eligible studies assent and 80% complete the survey at 3-months post-intervention, we will deem these data points as supportive of a hypothesis of feasibility.

The **acceptability** of program features (e.g., badges, Text Buddy) will be measured using 5-point Likert scales; average scores of 4 or more will be supportive of acceptability.⁹⁰ Youth engagement with the program will be examined to identify potential trends in greater intervention impact (e.g., for those who use the Text Buddy feature).

Post-intervention one-on-one interviews to illuminate the intervention experience will be analyzed using a thematic approach,⁹¹ as our aim will be more descriptive in nature, with a lower level of interpretation needed than is afforded by grounded theory or other qualitative analytical techniques.⁹²

Analyses examining **behavioral outcomes** will be primarily intended to inform power analyses for the larger R01. Data will be treated as intention-to-treat and complete case. We will conduct sensitivity analyses (e.g., missing = bullying behavior) to understand how this may affect our findings. Missing data that are not the main outcomes will be imputed.

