Baseline covariates will be examined to determine whether randomization performed as intended. Any that are significantly imbalanced across study arms will be included in multivariate analyses.

We will use logistic regression to analyze outcomes (e.g., bullying perpetration, other aggressive behaviors; bystander behavior). Once gross estimates of intervention effect have been calculated, covariates will be added to examine

whether they appear to mediate the relation between group assignment and the outcome. Three conditions must be met in order to claim that mediation is present:⁹³⁻⁹⁵ (1) a predictor (e.g., experimental arm) is significantly associated with a mediator (e.g., TPP motivation); (2) The mediator is significantly associated with an outcome (e.g., pregnancy); and (3) when one controls for the mediator, the effect of the predictor on the outcome becomes non-significant. If this effect retains significant but is attenuated, partial mediation is indicated. A 10% or greater change in the point estimate will be deemed clinically significant.^{96,97}

Sex as a biological variable. It is possible that males will respond to the program differently than females because it feels more individual and perhaps, in this way, will resonate more with males.⁸³ Conversely, perhaps because females text message at a greater volume than males,^{36,84} the format of this program may resonate more with them. As such, sex will be explicitly examined as a potential moderator. To understand whether the intervention impact varies by sex, we will test an interaction term, i.e., experimental group X sex. If the term is statistically significant, then it will suggest that boys and girls are impacted differentially by the intervention.

To examine whether/how the intervention effect attenuates over time, we will use generalized estimation equations to analyze the data across follow-up periods using an identity link and exchangeable correlation structure. By entering an interaction term for experimental group X time, we can determine if the intervention is differently impactful at intervention end versus 3-months post-intervention.

Should [name] need statistical guidance, we will take advantage of [name] access to the biostatistics 'core' at the University of North Carolina (please see Budget Justification).

Power analysis

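### Adjustment covariates are chosen by a baseline significance test that minimised factors practically never fail, and nothing commits the effect model to those factors or to baseline bullying

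*Combined protocol and SAP*

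**What the plan says.** Section 3C, Randomization and group assignment: youth are "randomly assigned to either the intervention (n = 76) or the control (n = 74) group", and "We will use a computerized minimization technique". On the factors it says only: "These may include sex, school or Club, and bullying perpetration history".

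Section 3E, Specific Aim 2, gives the covariate rule. Baseline covariates are examined to see whether randomisation worked, and then: "Any that are significantly imbalanced across study arms will be included in multivariate analyses". No significance level is given.

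The effect model is logistic regression with no covariate list. The other mentions of covariates do not fill that gap:

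- "Once gross estimates of intervention effect have been calculated, covariates will be added to examine" possible mediation, with the yardstick "A 10% or greater change in the point estimate will be deemed clinically significant".
- Sex enters a separate interaction test as a moderator.
- The GEE model names only a group-by-time term.
- Section 3C may add exposure questions as a proxy for contamination.

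Section 3E says that analyses of the behavioural outcomes "will be primarily intended to inform power analyses for the larger R01". The main outcomes are feasibility and acceptability.

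**The concern.** The two rules work against each other. Minimisation forces balance on the chosen factors, and section 3E then admits to the model only covariates that fail a balance test. The variables chosen for balancing are therefore the ones the rule leaves out. The plan does not forbid other adjustment. It simply does not prespecify any.

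This matters most for bullying history, the obvious predictor of later bullying. If it is minimised and then omitted, the standard error still allows for between-arm variation in baseline bullying that the design has removed. Intervals are then too wide, false positives too few and power too low. The fixed gross estimate does not depend on the selection rule, but it has the same conservative error.

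If bullying history is not minimised, the rule picks it up only about 5% of the time, so a useful predictor is usually left out. The covariates that the rule does select are mostly chance differences, chosen without regard to whether they predict the outcome. The later multivariate estimate then depends on which variables happened to differ.

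**Working it through.** The plan states no alpha, effect size or power for these outcomes, so there is no figure to reproduce.

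**Inputs from the plan.** 76 and 74 per arm (section 3C). Regular bullying 20–24% (section 1), with 22% used at baseline. 80% followed at 3 months (the section 3E feasibility criterion), so 0.80 × 150 = 120.

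**Assumed.** Two-sided 5% level. Follow-up bullying in baseline bullies versus others of 30/18, 40/15, 50/13, 60/10 or 70/8%. Conditional treatment odds ratio (OR) 0.4 for power.

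**Step 1. Can a minimised factor be flagged?** With t baseline bullies, a in intervention and b in control:

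z = (a/76 − b/74) / √[p(1−p)(1/76 + 1/74)], p = t/150.

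- t = 30 (20%): 20 v 10 gives z = 1.9598, just short of 1.96. 21 v 9 gives 2.37. In the other direction, 10 v 20 gives −2.12.
- t = 36 (24%): 24 v 12 gives 2.20. In the other direction, 13 v 23 gives −2.00.

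An arm difference of at least 10 is needed. In 4,000 simulated trials per scenario, deterministic minimisation never gave a difference above 3. With a 0.8 random element and 8 sites the largest was 8. The test was never significant in either case.

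**Step 2. Size of the conservatism, bullying history minimised.** Let R² be the share of outcome variance explained by baseline bullying:

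R² = 0.22 × 0.78 × (difference in follow-up rates)² / [p(1−p)], where p is now the overall follow-up rate.

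Full balance would make the true variance (1 − R²) times the reported one. Random loss of 20% restores about a fifth of the imbalance, so the factor is about 1 − 0.8R², and type I error ≈ 2Φ(−1.96/√(1 − 0.8R²)).

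Example, 70/8: p = 0.22 × 0.70 + 0.78 × 0.08 = 0.2164. R² = 0.1716 × 0.62² / (0.2164 × 0.7836) = 0.389. The factor is 0.689 and the type I error 1.8%.

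The simulation used 2,500 trials per setting, minimisation on sex, 3 settings and baseline bullying, and Wald tests. Type I error, %:

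| Baseline OR | Formula (unadjusted) | Simulated, unadjusted | Simulated, plan's rule | Simulated, prespecified adjustment |
|---|---|---|---|---|
| 2.0 | 4.9 | 5.0 | 4.9 | 5.5 |
| 3.8 | 4.4 | 3.9 | 4.2 | 4.8 |
| 6.7 | 3.7 | 3.4 | 3.6 | 4.9 |
| 13.5 | 2.8 | 2.5 | 2.6 | 4.7 |
| 26.8 | 1.8 | 1.7 | 1.8 | 4.2 |

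Monte Carlo standard error is about 0.4 points at 5%. A 0.9 biased coin gave the same pattern (unadjusted 4.6% at weak and 2.3% at strong prognosis).

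**Step 3. Power at treatment OR 0.4, %.**

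| Baseline OR | Minimised: rule / adjusted | Loss | Not minimised: rule / adjusted | Loss |
|---|---|---|---|---|
| 2.0 | 37.6 / 40.4 | 2.8 | 36.8 / 39.4 | 2.6 |
| 3.8 | 33.2 / 38.1 | 4.9 | 34.4 / 37.2 | 2.8 |
| 6.7 | 31.1 / 36.6 | 5.5 | 32.0 / 36.3 | 4.3 |
| 13.5 | 23.8 / 33.3 | 9.5 | 25.1 / 31.8 | 6.7 |
| 26.8 | 16.0 / 29.9 | 13.9 | 18.8 / 27.9 | 9.1 |

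When bullying history is not minimised, it is flagged in 4–6% of trials. Type I error is then 3.6–5.4% under the rule and 4.3–5.5% unadjusted.

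A second simulation used likelihood-ratio tests, 4,000 trials, baseline OR 3, 9 and 27, and treatment OR 0.3. With bullying history minimised, the rule gave type I error 4.5, 3.3 and 1.8%, against 5.0–5.1% adjusted, and lost 2, 8 and 17 points of power. Without minimising it, the losses were 1, 6 and 14 points.

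**Step 4. What the rule selects instead.** Section 3D lists about 25 non-minimised baseline variables: 11 social-emotional measures, victimisation, domestic violence, community violence, 2 alcohol items, literacy and 8 demographic or phone-use items. Expected number flagged: 25 × 0.05 = 1.25. If independent, P(at least one) = 1 − 0.95²⁵ = 0.72 (68–73% in simulation). Even with none of them prognostic, the multivariate OR differed from the gross OR by 10% or more in 26–30% of trials (minimised) or 27–35% (not minimised). The significance verdict differed in 1–7%.

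**The case against.** The strongest reply is that the significance-test rule does little harm itself. Compared with no adjustment at all it costs only 0 to 1.4 points of power, and the rest comes from leaving out baseline bullying. That is right. It means that deleting the rule is not enough and that the covariates must be named.

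Next, the behavioural outcomes are preliminary, no power is claimed, and power is about 40% at best with either analysis. This stands. It limits the matter to a recommendation, and no bias in the gross estimate is alleged. But the stated use of these estimates is R01 planning, which needs a stable estimate, an honest interval and a clear statement of which odds ratio is meant.

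Third, the size rests on a prognostic strength that the plan does not give, and the conservatism requires bullying history to be minimised, which is only a possibility. Both are true. At baseline OR 2.0 the difference is minor.

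Fourth, the 10% yardstick is stated for mediation. That is so, and with a standard error of about 0.46 on the log odds ratio, a 10% change is only ln(1.1)/0.46 ≈ 0.2 standard errors. The figure shows instability, not a changed conclusion. The 25 variables also overlap in content, so the 68–73% depends on assuming independence.

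Finally, a type I error of 3.6% appears both where the analysis is called conservative and where it is called about right. The comparator separates them. Adjustment gives 4.9% in the first case, so the deficit comes from the omission. It gives 3.8% in the second, so the rule is not the cause.

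**Conclusion.** The concern holds. A minimised factor will in practice never be selected, though this is not a logical certainty because the minimisation algorithm is not described. No other text commits the effect model to the minimisation factors or to baseline bullying.

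If bullying history is minimised, the analysis is conservative, from negligibly so at weak prognosis to a type I error near 2% at very strong prognosis, with about 3 to 14 points of power lost at treatment OR 0.4. If it is not minimised, error rates are about right and about 3 to 9 points are lost.

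These sizes assume a 5% level, 22% baseline bullying, 80% random follow-up and the range of prognostic strength shown. The change should be made, but it does not touch the feasibility and acceptability outcomes.

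**What to change.** Delete the significance-test rule and show baseline balance descriptively only. For each behavioural outcome, prespecify one short logistic model: arm, baseline bullying perpetration, and the minimisation factors actually used. Pool sites to school, Club or online, and name a penalised fit in case events are few.

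- **Perpetration and other aggression:** enter baseline status as none, other aggression or bullying.
- **Bystander behaviour:** do not require the baseline response. Table 3 asks it only of youth who saw or heard about bullying ("Those who say yes will be asked what they did in response"). Either omit it or code it with a category for having witnessed none, so that no youth is dropped.
- **Reporting:** give a standardised marginal effect beside the gross estimate, and say which one the R01 will be planned on, because adjusted and unadjusted odds ratios are different quantities.

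The cost is SAP wording and one coding rule. No new data are needed, since the baseline survey precedes randomisation.

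The limit is the number of events, about 18–26 among 120. The model has 5 terms with binary baseline bullying (arm 1, bullying 1, sex 1, setting 2) and 6 with the three-level status. Only the binary form was used in the simulations tabulated above, and neither the penalised fit nor the bystander model was simulated. The list must stay short: in the second simulation, with 8 unpooled sites, adjusting for all the factors raised the likelihood-ratio type I error to 7.5%.

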Specific Aim 2: Pilot test the 7-week BullyDown primary prevention program for feasibility and acceptability in an RCT of 150 middle adolescents. Youth will be randomly assigned to either BullyDown, a 4-message-per-day program, or an attention-matched control group talking about ‘healthy lifestyle’ topics (e.g., exercise). Our main outcome measures will be feasibility (e.g., recruitment and enrollment rates) and acceptability (e.g., positive program appraisal) at intervention end. The behavioral outcomes we will measure to motivate power analyses for a future R01 include: (1) bullying perpetration, (2) other aggressive behavior directed towards peers, and (3) bystander behavior in the past 30 days at 3-month post-intervention. We also will examine behavioral indicators at intervention end to observe proximal effects.

Given the limited impact of existing school-based interventions and the time associated with implementing them during school time, more efficient and effective intervention methods are needed. Programs that can be delivered to youth in middle adolescence, typically of middle school aged, irrespective of whether they are attending school physically or virtually may be especially relevant as school boundaries become more fluid. BullyDown addresses this critical need by providing a scalable program that could be quickly and cost-effectively disseminated nationally. If efficacious, we will test the intervention in an R01-funded RCT. Future endeavors could include adapting the program for Spanish-speaking youth and dynamically tailoring content to reported bullying behaviors.

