FGs will be conducted over multiple days on CiPHR's highly interactive, bulletin board-style, password-protected website. This online data collection space has been fully vetted for acceptability and feasibility among adolescents in [name]'s previous projects with adolescents.⁵¹⁻⁵⁷ We will ask participants to log on 2-3 times per day at their convenience and respond to moderator questions and comments from other participants.

Example questions include: Now that you are going to school online, how has this changed the way you talk with other kids in your class? How does bullying look different now than when you went to school in-person? Share an example of how someone was bullied in class this past week. What did other kids do? What did your teacher do? Questions will be updated to reflect the academic setting when we are in field.

Krueger and Casey⁵⁸ recommend 3-4 FGs per participant category. Online FGs can accommodate more participants, such that they typically include about 20 participants. Because one or two FGs are needed to match a commensurate sample size as in-person FGs, we plan to conduct about three FGs. We expect coding stability and theoretical saturation, the point at which emerging ideas are repetitive and do not substantively alter the themes developed from initial interviews, to be achieved after the two FGs. If saturation has not occurred, we will conduct additional FGs.

Please see **Data Analysis** for more information.

We will monitor the Boards closely for inappropriate behavior but anticipate that the online format will facilitate the feeling of a safe place and ability to be open and honest about one's experiences.

[name] will review the current content and identify opportunities to update it based upon the FG data. We anticipate examples and scenarios will be expanded to refer to online interactions more directly. To remain within the 4 message per day frequency, an additional week of messaging may be added, based upon how many messages can be simply adapted versus added. Once a draft is ready, [name] will review and provide feedback. [name] will integrate the feedback and then send the revised content back to [name] for review. This process will be iterative until they agree that the relevant themes have been well integrated.

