Data collection. Measures will be collected online at baseline, intervention end, and 3 months post-intervention end. All participants, regardless of study condition, will complete assessments at each time point. Youth will be able to complete the surveys on their own (e.g., at home). If they are attending the brick and mortar school or Club, they also will be able to complete the survey at school or Club in the computer lab if they would prefer. To facilitate self-completion, youth will receive an invitation text message with a unique URL to access the survey. This allows participants to complete the survey at a time and place convenient for them. Alternatively, they can sign up for one of the survey sessions at school or Club that the research staff will schedule with the school or Club administration. To avoid unintentional influence that school and Club staff may have on youth survey answers, only research staff will be present in the computer lab during survey administration.

3D. MEASUREMENTS AND STUDY INSTRUMENTS

Most of the proposed measures below were used in the beta test, suggesting the survey length can be feasibly completed by adolescents in middle school or between the ages of 12-14 year of age. Measures are as follows:

Table 3. BullyDown assessment measures		
Main Outcome measures (intervention end)	Acceptability	We will measure intervention acceptability and tolerability ⁶⁷ with a combination of open-ended questions (e.g., “What aspect of the program did you like the least?”) and questions that form a scale of intervention acceptability (e.g., I liked my Text Buddy; $\alpha = .87$). Participants will estimate the number of messages they received in the past week and percent that they read. The program will record the number of weekly level-up questions answered, and the number answered correctly, as well as the number of Text Buddy and Forever Friend messages sent.
	Feasibility	We will monitor the number of eligible/ineligible youth, the number of parental permission forms received, the number of youth invited but who decline to take part, and the retention rate.

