Exogenous variables include: 1) **SEL components:** Communication – youth will be presented with four different scenarios and asked to identify whether it reflects passive, aggressive, or assertive communication. Causey & Dubow's Self-report Coping Measure will be used to measure stress coping and problem-solving. Both are 8-item subscales with acceptable reliability ($\alpha = 0.84$ and $\alpha = 0.84$, respectively). Problem-solving asks youth how often they, for example, “Change something so things will work out.” Empathy will be assessed with the 5-item Empathy subscale in the Teen Conflict Scale ($\alpha = .62$).⁶⁹ Respect for diversity will be measured with the 4-item Support for Cultural Pluralism subscale of the Inventory of School Climate ($\alpha = 0.68$).⁷⁰ Identifying bullying will be measured by showing participants various “features” and asking them to identify those that reflect bullying (i.e., repetitive, with differential power, intent) Attitudes towards bullying and aggression will be measured with the 4-item University of Illinois Positive Attitudes toward Bullying Scale ($\alpha = 0.81$).⁷¹ Bystanders’ intentions will be measured with the 5-item University of Illinois Willingness to Intervene scale ($\alpha = .62$).⁷² Anger and hostility will be measured with the University of Illinois Anger Scale ($\alpha = .81$; e.g., “I got in a physical fight because I was angry”).⁷³ Hostility will be measured with the Symptom Checklist-90 subscale, which is a 6-item scale ($\alpha = .87$).⁷⁴ Impulsivity will be measured with the 4-item Impulsivity subscale from the Teen Conflict Survey ($\alpha = .62$).^{75,76} 2) **Peer victimization:** Victimization questions that mirror the bullying questions described will be asked of all youth. Those who say they have been victimized in at least one way 3 or more times in the past 30 days, by someone with more power than them, will be coded as being bullied. Those who report less frequent victimization and/or an aggressor with equal power will be coded as a victim of other aggressive acts. 3) **Exposure to domestic violence** will be measured using an item from the Juvenile Victimization Questionnaire (JVQ).⁷⁷ This well-

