4. PROTECTION OF HUMAN SUBJECTS

Ethical considerations

The study will be conducted according to ethical principles stated in the Declaration of Helsinki (2013). IRB approval will be obtained before initiating the study. Assent and permission forms will take into consideration the well-being, free-will and respect of the participants, including respect of privacy.

Sources of Information.

RCT measures will be collected at baseline, intervention end, and 3-months post-intervention end in online surveys. All participants, regardless of study condition, will provide data at each time point. FG and CAT data will be collected online.

4.a. Potential Risks

The largest risk posed by participation in the study is inadvertent loss of confidentiality of one's bullying behavior or experiences. Confidentiality also may be lost if someone sees the participant's computer screen or intercepts his/her cell phone and reads the text messages. It is possible that survey questions or intervention topics may cause discomfort for some youth. It also is possible that conversations between Text Buddies will be harmful (e.g., bullying) in the RCT. Finally, it is possible that participants in the focus groups might be in the same online focus group as their bully.

4.b. Adequacy of Protection against Risks

The researchers take these potential risks very seriously. The PI will be responsible for all aspects of the project with respect to intervention design, data collection, and use of data. All aspects of the study will be approved by Pearl IRB, the Center for Innovative Public Health Research (CiPHR)'s OHRP-approved IRB of record prior to commencing data collection.

Informed Youth Assent and Caregiver Permission.

Youth assent and parental permission forms will receive final approval from the IRB before going into field. The assent information will be discussed with the participant by study staff either online, or at school or BCGA Clubs if youth are back in person. who are trained in Human Subjects Protections. Participants will be given the opportunity to ask any questions. They will be told that they can choose not to participate without any consequence. Given that children are a

vulnerable population, we also will be collecting active parental permission.

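### Mediation is claimed with no required time order: intervention-end outcomes have only a same-survey mediator, and the well-ordered pairing available for the 3-month outcome is not specified

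*Combined protocol and SAP*

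**What the plan says.** Section 3E (Specific Aim 2) fits logistic regressions of the behavioural outcomes on arm, then adds covariates to see "whether they appear to mediate the relation between group assignment and the outcome". A mediation claim needs three things: arm is associated with the mediator, the mediator is associated with the outcome, and the arm effect loses significance once the mediator is controlled. An effect that shrinks but stays significant counts as partial mediation. A change of 10% or more in the point estimate is treated as clinically meaningful. No condition concerns timing. The section does not say which survey supplies the mediator, and its examples (a motivation score and pregnancy) belong to another topic.

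The schedule is stated twice and consistently. Section 3C: "Measures will be collected online at baseline, intervention end, and 3 months post-intervention end". Section 4, Sources of Information: "RCT measures will be collected at baseline, intervention end, and 3-months post-intervention end in online surveys".

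Table 3 in section 3D sets the outcome time points, "Preliminary behavioral outcome measures (Intervention end and 3-month follow-up"), and codes bullying perpetration as follows: "Youth who endorse any question at a frequency of 3 times or more in the past 30 days". The SEL measures are listed after Table 3 among the exogenous variables, with no schedule of their own. One of them, the Anger Scale, is illustrated by the item "I got in a physical fight because I was angry".

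On programme length, section 2 has "Pilot test the 7-week BullyDown primary prevention program", and section 3C allows that "an additional week of messaging may be added".

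**The concern.** A mediation claim asserts a sequence: the programme changes a skill or attitude, and that change alters behaviour. Adding a covariate and watching the arm coefficient shrink cannot separate this sequence from its reverse, in which behaviour changes and the score follows. Time order is the main protection the data could offer, and the plan does not ask for it.

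A baseline score cannot mediate, because it precedes allocation. That leaves the intervention-end and 3-month scores. For the intervention-end outcome, any usable score sits in the same questionnaire as the outcome. For the 3-month outcome, an analyst could use either the intervention-end or the 3-month score and still follow the plan.

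The Anger Scale adds a smaller problem. An item recording a fight may share content with the physical aggression items it would be used to explain, so some of the association could come from overlap in measurement.

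At stake is whether a statement that a given SEL skill mediated the effect can be believed.

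**Working it through.** The plan gives no power calculation or expected mediation effect, so there is no figure of its own to reproduce.

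**1. Timeline**

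Inputs: programme of 7 weeks (49 days), possibly 8 (56 days); recall of 30 days; follow-up 3 months after programme end (about 91 days).

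- Intervention-end outcome, 7 weeks: window opens at day 49 − 30 = 19, so it covers days 19 to 49.
- With 8 weeks: 56 − 30 = 26, so days 26 to 56.
- A survey completed 7 days late still has 30 − 7 = 23 of its 30 days inside the programme.
- 3-month outcome: window opens 91 − 30 = 61 days after programme end.

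The intervention-end score is therefore taken at the close of the window for the intervention-end outcome, and about two months before the window for the 3-month outcome opens.

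**2. Size of a spurious shift**

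Assumptions, none given by the plan except that 22% lies inside the 20–24% background range in section 1:

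- Bullying is 22% in control and 11% in intervention.
- The score is M = −d·arm + g·Y + N(0,1), with higher M meaning worse. The programme improves it by d SD. Having bullied (Y = 1) worsens it by g SD.
- M has no effect on Y, so true mediation is zero.

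Unadjusted OR = (0.11/0.89) / (0.22/0.78) = 0.438; log OR = −0.825.

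By Bayes' rule, logit P(Y | arm, M) = logit P(Y | arm) + g(M + d·arm) − g²/2. The adjusted arm coefficient is therefore log OR + g·d.

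| g | d | g·d | Adjusted OR | Change in OR | Share of log OR |
|---|---|---|---|---|---|
| 0.8 | 0.5 | 0.40 | exp(−0.425) = 0.654 | 49% | 0.40/0.825 = 48% |
| 0.5 | 0.3 | 0.15 | exp(−0.675) = 0.509 | 16% | 0.15/0.825 = 18% |
| 0.3 | 0.2 | 0.06 | exp(−0.765) = 0.465 | 6% | 0.06/0.825 = 7% |

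The first two rows pass the 10% rule and the third does not, on either scale.

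**3. The three conditions at the trial's size**

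I simulated the same model at 76:74 (4,000 trials per row). The plan gives no significance level, so I assumed two-sided 0.05 and required a significant unadjusted arm effect. Full or partial mediation was falsely declared as follows:

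| g, d | Of all trials | Of trials with a significant arm effect |
|---|---|---|
| 0.8, 0.5 | 38% | 90% |
| 0.5, 0.3 | 16% | 38% |
| 0.3, 0.2 | 4% | 9% |
| 0, 0.5 (no reverse effect) | 1% | 2% |

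The columns differ because the arm effect is significant in only about 42–43% of trials.

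**4. Other reverse-only models**

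Suppose instead that the frequency of behaviour drives both the coded outcome and the score, and the programme has no separate effect on the score. Across control/intervention rates of 22/11%, 22/5% and 40/15%, at 76:74 and 61:59 (about 80% retention):

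- Correlation 0.3: the arm log OR shrank by a median of 3–4%; mediation was declared in 8–22% of trials with a significant arm effect.
- Correlation 0.5: 11–14% and 30–72%.

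If the score depends only on the yes/no outcome with no separate programme shift (d = 0), then g·d = 0 and there is no systematic shrinkage. Any declarations are sampling noise.

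**The case against.** Several objections have force.

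- **Mediators not named.** The plan never calls the SEL scores mediators; section 3D lists them as exogenous variables. Treating them as the intended mediators is an inference from the SEL model in section 2. It is a reasonable one, but a reader should not take it that the plan commits to same-survey SEL mediators. It leaves the wave open.
- **Order is ambiguous.** A reader might infer that the intervention-end mediator necessarily follows the behaviour. The documents do not support that. Section 3D gives no recall period for these scales, and a skill gained early in the programme would still be present at its end. For recognition tasks, such as classifying communication styles, a reverse effect is less plausible. What stands is that direction cannot be established.
- **The main behavioural time point can be handled.** Section 2 places the behavioural outcomes at 3 months and treats intervention end as a look at proximal effects. The 3-month outcome has a well-ordered mediator available, so not all planned mediation is invalid.
- **Consequences are limited.** It is tempting to say that the result decides what the later programme retains. The documents do not say so. Section 3E says the behavioural analyses mainly inform power for the next trial, and the main outcomes are feasibility and acceptability.
- **The anger item is not the outcome.** Fighting from anger is one example item. The coded outcome is bullying acts at a set frequency. Overlap is possible, but identity is not shown.
- **The size is assumed.** The 49% figure needs both a 0.8 SD reverse effect and a 0.5 SD programme shift; milder values fall below the 10% rule.

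The weekly level-up answers recorded during the programme do not fill the gap. Table 3 lists them as acceptability data, not SEL scores.

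**Conclusion.** The point holds as a gap in the analysis rule. Section 3E lets a variable be called a mediator with no time-order condition. With the three planned surveys, no post-randomisation SEL score precedes the intervention-end outcome window, so a mediation claim for that outcome cannot be separated from a reverse effect. For the 3-month outcome, a well-ordered mediator is already in the data but is not specified. Changing the estimator of the indirect effect would not cure this, because the ambiguity lies in the timing of the data.

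On the assumptions in the working, the arm odds ratio moves by 6% to 49% with no true mediation. These figures show that the rule does not exclude the error; they do not predict how often it will occur. Because mediation is secondary and exploratory in a feasibility pilot, this is a cheap improvement and not a threat to the trial's main conclusions.

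**What to change.** In section 3E:

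1. Name the mediators, replacing the examples carried over from another topic.
2. Limit mediation claims to one sequence: arm, then intervention-end SEL score, then 3-month outcome, adjusted for the baseline SEL score and baseline bullying.
3. Report all same-survey results, including every one for intervention-end outcomes, as associations only.
4. Adjust for bullying at intervention end only as a sensitivity analysis. It is post-randomisation and may lie on the pathway, so adjusting for it can hide real mediation.
5. When the Anger Scale is tested as a mediator of bullying or aggression, add a sensitivity analysis without aggressive-act items such as the fight item. Keep the full scale as the main version, since the quoted reliability applies to that.

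The cost is wording; no new data are needed. The mediation claim at intervention end is given up. Youth who miss the intervention-end survey stay in the 3-month survey (section 3C), but their mediator scores then rely on the imputation in section 3E. Estimates will be imprecise: at the assumed rates, expected events are 76 × 0.11 + 74 × 0.22 ≈ 25 with full follow-up and 61 × 0.11 + 59 × 0.22 ≈ 20 at 80% retention, for a model with four terms. Confidence intervals should therefore accompany any mediation result.
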